Virtual Reality for Improving Pain and Distress in Patients with Advanced Stage Colorectal Cancer

(VR Blue)

Pro00103248

NCT04069702

July 30, 2021

Purpose of the Study

Aim 1: Examine the feasibility, acceptability and safety of a 30-minute VR Blue session in patients with advanced colorectal cancer.

Hypothesis: Feasibility will be determined by accrual (N=20 patients over 6 months), >80% adherence to the protocol (defined as the degree to which participants are willing and able to complete the 30-minute VR exposure), and >80% completed data (measured by percent data collected at the study appointment, including pre-, midpoint, and post-VR assessments). Acceptability will be demonstrated by 80% of participants reporting VR satisfaction on the Client Satisfaction Questionnaire (mean score of 7/8). Safety of the VR protocol will be demonstrated by 80% of participants completing the VR session without significant side effects, such as motion sickness, dizziness, headache, and nausea.

Aim 2: Collect initial data on the impact of VR Blue on pain, tension and distress, and describe the relationship between pre- to post-VR changes in cognitive variables (i.e., pain catastrophizing, pain self-efficacy) and changes in pain, tension and distress over the course of the VR session.

Hypothesis: 2A. Reductions in pain, tension and distress will be demonstrated during the VR session in colorectal cancer patients. 2B. Pre- to post-VR reductions in pain catastrophizing and increases in pain self-efficacy will be correlated with improvements in pain, tension and distress occurring over the course of the VR session.

Aim 3: Gather qualitative post-session data on patients' experiences, thoughts and feelings about VR to optimize VR Blue for a future randomized clinical trial testing a multi-session VR protocol.

Hypothesis: This data will lead to optimization and manualization of a multi-session VR Blue protocol to manage pain in advanced colorectal cancer patients that can be tested in a larger, randomized clinical trial.

Background & Significance

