Procedures. Study Appointment. The study appointment will take place at the Duke Pain Prevention and Treatment Research Program office. At this appointment, research staff will explain study procedures and conduct informed consent. Once informed consent is obtained, patients (N=20) will complete the pre-VR assessment (<30 min) via REDCap, a HIPAA/PDPA compliant, web-based survey system. Following completion of this assessment, participants will complete the VR exposure and the midpoint assessment. Participants will then complete the post-VR assessment immediately following VR Blue exposure. Participants will be compensated \$40 for completing this study appointment. Participants will continue to receive usual care and will not be asked to change or decline any strategies for pain management.

Virtual Reality Exposure. We will gather preliminary data on participants' response to a single 30-minute laboratory-based virtual reality underwater/sea environment (VR Blue) session. VR Blue is an immersive computer-generated environment featuring calming scenic graphics and relaxing nature music. VR Blue has been shown to increase tolerance for thermal pain stimuli in healthy participants by [name], consultant on this application. In the proposed study, a member of the study team will familiarize the participant with the VR glasses and screen, and guide them through a demonstration of the VR environment. Participants will be oriented to the VR's video and auditory stimuli with an emphasis on becoming relaxed and fully immersed in the virtual environment. Participants will be instructed to pay close attention to the virtual environment around them to cultivate their awareness of what they see. Following this orientation, the participant will complete the 30-minute VR exposure. At the midpoint, participants will be asked to provide ratings of pain, tension and distress.

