Study Measures. Aim 1: Feasibility will be assessed by examining (a) study accrual (N=20 over 6 months), (b) protocol adherence (>80% adherence to the protocol [defined in this study as the degree to which participants are willing and able to complete the 30-minute VR exposure]), and (c) completed data (>80% data collected at the study appointment, including pre-, midpoint, and post-VR assessments). Acceptability will be assessed post-VR using the Client Satisfaction Questionnaire.³¹ Safety of the VR protocol will be assessed based on participants' report of VR side effects, such as motion sickness, dizziness, headache, nausea, or other negative physical reactions. Aim 2: Pre-, midpoint- and post-session ratings of pain, tension, stress, anxiety, and mood. Pain. Pain will be assessed using the Brief Pain Inventory (BPI) measuring pain severity and interference. This measure has been widely used in cancer patients. Tension, Stress, Anxiety and Mood. Tension, stress, anxiety and mood will be measured with Visual Analogue Scale (VAS) items with ratings ranging from 0 to 100. The timeframe reference will be "right now". VAS's for measuring tension, stress, anxiety and mood have been used in prior VR studies. Pre- and post-session measures of expectancy and enjoyment. We will use Visual Analogue Scale (VAS) items with ratings ranging from 0 to 100 to measure how much participants expect to improve from participating in the VR Blue intervention (pre) and how much they enjoyed participating in the VR Blue intervention (post). Pre- and post-session measures of pain catastrophizing and self-efficacy for pain. Pain Catastrophizing. Pain catastrophizing will be measured with the Coping Strategies Questionnaire's Pain Catastrophizing subscale. The timeframe reference will be "right now". Items will be rated on a scale ranging from 0=never do to 6=always do when in pain. Pain Self-Efficacy. Self-efficacy will be measured using items adapted from the self-efficacy for pain management subscale of the Chronic Pain Self-Efficacy Scale. For example, participants will be asked, "How confident are you that you could use virtual reality to decrease your pain?" Items are rated on a 10-point scale ranging from 10=very uncertain to 100=very certain. Scores are averaged to give an overall value for pain self-efficacy. Aim 3: We will conduct exit interviews with participants to collect qualitative data to refine and improve the VR protocol.

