Data Analysis and Statistical Considerations. Analyses for Aim 1. Feasibility will be assessed by examining accrual, adherence and data completion. Accrual will be indicated by meeting the recruitment goal of 20 participants in 6 months. Descriptive statistics will be used to report the number of patients screened and determine rates of non-eligibility and refusal. Adherence for patients who are accrued to the study will be examined by calculating the degree to which participants are willing and able to complete the 30-minute VR exposure. 80% completed will serve as our feasibility benchmark. If less than 20% of consented patients complete the 30-minute VR exposure, the VR Blue protocol will not be considered feasible. Data completion will be measured by percent data collected at the study appointment, including pre-, midpoint and post-VR exposure assessments. 80% completed data will serve as our feasibility benchmark. If less than 20% of consented patients have complete data, the VR Blue protocol will not be considered feasible. Acceptability will be indicated by 80% of patients reporting satisfaction with VR Blue (mean score of 7 out of a total 8) on the Client Satisfaction Questionnaire. Safety of the VR protocol will be demonstrated 80% of participants completing the VR session without significant side effects, such as motion sickness, dizziness, headache, nausea, or other negative physical reactions. Analyses for Aim 2. We will examine descriptive data to explore pre-, midpoint and post-VR exposure changes in pain, tension and distress scores. We will cautiously examine these differences in the context of minimally clinically important differences (MCIDs) for pain, tension and distress (e.g., 30% decrease in pain).³⁶⁻³⁹ Correlations will be conducted to provide preliminary data on how pre- to post-VR changes

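### Pain catastrophizing pairs a 'right now' timeframe with frequency anchors, so its sensitivity to change over one 30-minute session is doubtful and the catastrophizing half of Hypothesis 2B is weakened

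*Combined protocol and SAP*

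**What the plan says.** Study Measures (Aim 2) names the instrument: "Pain catastrophizing will be measured with the Coping Strategies Questionnaire's Pain Catastrophizing subscale". The next sentence sets a momentary frame, "The timeframe reference will be 'right now", and the one after it gives the response scale: "Items will be rated on a scale ranging from 0=never do to 6=always do when in pain".

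The scale is given twice, under the label "Pre- and post-session measures of pain catastrophizing and self-efficacy for pain". On the second occasion, according to Procedures, "Participants will then complete the post-VR assessment immediately following VR Blue exposure".

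Hypothesis 2B in Purpose of the Study uses the difference between those two occasions: "Pre- to post-VR reductions in pain catastrophizing and increases in pain self-efficacy will be correlated with improvements in pain, tension and distress". The Aim 2 analysis follows suit: "Correlations will be conducted to provide preliminary data on how pre- to post-VR changes" in the two cognitive variables relate to improvement in pain, tension and distress.

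For the other cognitive variable, pain self-efficacy, "Items are rated on a 10-point scale ranging from 10=very uncertain to 100=very certain".

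**The concern.** The timeframe and the anchors ask different questions. 'Never' and 'always' are frequencies over occasions, and 'when in pain' generalises over pain episodes; neither end of the scale describes a single moment. A patient guided by the anchors reports a habit, which there is little reason to expect to shift in half an hour. A patient guided by the timeframe has to translate a momentary state into a frequency. Some patients may do one and some the other, or the same patient may do one before the session and the other after it.

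At stake is the pre-to-post change score for one of the two cognitive variables in Aim 2. If that score is compressed or noisy, its correlation with change in pain, tension and distress is harder to read. A weak result could mean that catastrophizing does not move with symptoms during VR, or only that the scale did not ask about the session. Because the pilot is meant to inform a multi-session protocol, that ambiguity would carry forward.

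**Working it through.** The plan states no reliability, standard deviation, target correlation or power for this measure or for Hypothesis 2B, so it has no figure to reproduce. The check is mainly one of wording.

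**Step 1. Compare the Aim 2 self-ratings in Study Measures.**

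| Measure | Timeframe stated | Response format |
|---|---|---|
| Tension, stress, anxiety, mood | right now | 0-100 visual analogue scale |
| Pain self-efficacy | none stated | 10-100, very uncertain to very certain |
| Pain catastrophizing | right now | 0-6, never do to always do when in pain |

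Only catastrophizing joins a momentary timeframe to frequency anchors. The other ratings given a 'right now' timeframe are on visual analogue scales with no frequency wording described.

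**Step 2. Set the anchors against the interval.** The score needed is post minus pre across one 30-minute exposure, with the second rating taken straight afterwards. There are three ways of responding:

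- Both ratings by habit: expected change is near zero. If every patient did this exactly, all changes would be 0 and the correlation would be undefined.
- Both ratings for the moment: real change can appear, through labels that do not fit.
- A different reading on each occasion: the difference contains the switch as well as any real change.

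The documents do not show which of these would predominate.

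**Step 3. Check whether 'when in pain' amounts to 'right now' here.** Recruitment asks for pain on most days over 3 months, so the two often overlap. They need not coincide after the session if VR eases pain. Selection of Subjects also lets patients proceed with pain below 4/10 on the day. (Recruitment requires a yes to the day-of-appointment pain question; those two passages need reconciling separately.)

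**Step 4. Illustrate the possible attenuation.** Assumptions, none from the documents: the true correlation between change in catastrophizing and change in pain is 0.5; pain change is measured without error; and the catastrophizing change score has reliability 0.2, 0.3 or 0.5. The formula is observed r = true r × √reliability.

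- 0.5 × √0.2 = 0.22
- 0.5 × √0.3 = 0.27
- 0.5 × √0.5 = 0.35

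**Step 5. Put these beside sampling error at N = 20.** The Fisher interval is tanh(atanh r ± 1.96/√(20 − 3)), and 1.96/√17 = 0.475.

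| Observed r | Approximate 95% interval |
|---|---|
| 0.50 | 0.07 to 0.77 |
| 0.35 | −0.11 to 0.69 |
| 0.27 | −0.20 to 0.64 |
| 0.22 | −0.25 to 0.60 |

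The intervals overlap heavily. On these assumptions the unattenuated value excludes zero and the attenuated ones do not, but the study could not reliably distinguish the cases.

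**The case against.** The strongest reply is that the protocol saw the time-window problem and dealt with it by setting the timeframe to the present moment. The instruction is the same at both assessments, so a patient who applies it consistently gives a usable difference. The items and the REDCap form are not in the documents, so the wording patients see may be better than the one-sentence summary. Most of these patients live with pain, so 'when in pain' often describes the present. With 20 patients, any correlation will be imprecise even on a perfect scale, and the proposed replacement anchors come with no responsiveness data either.

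Much of this stands, and it limits the point. A reader might infer that the scale cannot register change at all. The documents do not support that: they contain no responsiveness or reliability data, and the momentary instruction leaves room for ratings to move. A reader might infer that Hypothesis 2B as a whole fails. It does not, because it also uses pain self-efficacy, which this point leaves untouched. A reader might also infer that the trial would wrongly abandon the cognitive pathway. The plan has no rule for doing so; Aim 2 is descriptive, its correlations are labelled preliminary, and the stated benchmarks belong to Aim 1.

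What the reply does not remove is the conflict between two adjacent sentences. Adapting the timeframe while keeping frequency anchors leaves the adaptation half done, and nothing in the plan says how the anchors should be read under it. A small sample is no reason to accept avoidable noise.

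**Conclusion.** The concern holds as a mismatch between timeframe and response scale. The scale's sensitivity to change over one 30-minute session is doubtful, and the documents offer nothing to support it. The catastrophizing correlations in Aim 2 are weakened to an unknown degree, and a weak one could not be attributed to the construct rather than the scale.

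The figures of 0.22 to 0.35 show how attenuation would work under assumed inputs. They are not an estimate of what this trial will observe, and they do not measure the gain from rewording, since the reliability of a reworded scale is also unknown. The judgement rests on the anchors reaching patients as Study Measures states them; if the form words them differently, the protocol should say so. This is worth correcting because correction is cheap, but it concerns one exploratory component of a pilot and does not touch the Aim 1 conclusions.

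**What to change.** Keep the subscale items and the 'right now' stem. At both the pre-VR and post-VR assessments, replace the anchors with a momentary scale, for example 0 = not at all true right now to 6 = completely true right now. Describe the measure in Study Measures as an adapted state version of the subscale, and give the wording used.

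The cost is a change of response labels in REDCap and of a sentence in the protocol, with no added visits, patients or burden. The downside is that scores will not be comparable with the unadapted scale. No planned analysis makes that comparison, and the 'right now' stem already departs from a habitual reading.

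If data have already been collected, do not relabel afterwards. Report the exact stem and anchors patients saw, and interpret the catastrophizing correlations with caution, stating that a weak one may reflect the scale.

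### Aim 1's feasibility rules are inconsistent: data completion passes and fails in different units, the 80% threshold has two signs, and results between 20% and 80% have no stated verdict

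*Combined protocol and SAP*

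**What the plan says.** Three places in the combined protocol and SAP set the Aim 1 feasibility rules.

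- **Purpose of the Study, Aim 1** gives the criterion: "Feasibility will be determined by accrual (N=20 patients over 6 months), >80% adherence to the protocol". It also asks for more than 80% completed data, measured as percent of data collected.
- **Design & Procedures, Study Measures, Aim 1** repeats the strict threshold for both quantities. For data it reads "completed data (>80% data collected at the study appointment, including pre-, midpoint, and post-VR assessments".
- **Design & Procedures, Data Analysis and Statistical Considerations, Analyses for Aim 1** drops the strict sign and adds failure rules.
  - Adherence is examined by "calculating the degree to which participants are willing and able to complete the 30-minute VR exposure". The benchmark is "80% completed will serve as our feasibility benchmark", and the failure rule is "If less than 20% of consented patients complete the 30-minute VR exposure, the VR Blue protocol will not be considered feasible".
  - For data, "Data completion will be measured by percent data collected at the study appointment". The benchmark is "80% completed data will serve as our feasibility benchmark", and the failure rule is "If less than 20% of consented patients have complete data, the VR Blue protocol will not be considered feasible".

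The planned sample is 20 patients. Accrual has a single criterion and is not affected by this point.

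**The concern.** A plan that fixes pass and fail rules in advance should give one verdict for each possible result. Here there are three obstacles.

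1. The data-completion benchmark counts data, while its failure rule counts patients.
2. The same threshold is strict in two sections and unsigned in the third.
3. Failing to exceed 80% misses the criterion that determines feasibility, yet the only statement that the protocol is infeasible applies below 20%. A reader cannot tell what label a result between the two receives.

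At stake is the Aim 1 feasibility conclusion. Where the rules give two answers, or none, the label would have to be chosen after the data are seen.

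**Working it through.** The plan states no operating characteristics and no sample-size derivation, so there is no figure to reproduce. The check turns the stated percentages into counts and then asks what each rule concludes.

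**1. Data completion: units**

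Study Measures lists five ratings taken before, at the midpoint of and after the session: pain, tension, stress, anxiety and mood. Count the Brief Pain Inventory as one rating and leave out the measures taken only before and after (simplifying assumptions).

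- Ratings per patient: 5 × 3 = 15. In total: 15 × 20 = 300.
- Suppose 17 patients each miss one rating. Collected: (300 − 17)/300 = 283/300 = 94%, so the 80% benchmark is met.
- Patients with complete data: 3/20 = 15%, below 20%, so the failure rule is triggered.

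This example is constructed. It shows that the clash is possible, not that it is likely. How easily it arises depends on how many items count towards complete data, which the plan does not define. With K items per patient, each missing independently with probability m, a patient is complete with probability (1 − m)^K. At m = 5% (95% of data collected on average), the chance that 3 or fewer of 20 patients are complete is 4% for K = 20, 35% for K = 30 and 75% for K = 40. Both K and m are assumptions.

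**2. Counts out of 20**

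Assume each patient is scored complete or not.

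- More than 80% means at least 17 patients.
- 80%, read as a benchmark reached, means at least 16.
- Less than 20% means at most 3.

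So 16/20 misses the threshold in Purpose and Study Measures and meets the one in the analysis section. Results of 4 to 15 fall short of the benchmark under either sign and do not trigger the failure rule. Under the strict sign that range is 4 to 16.

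**3. How often each result occurs**

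Exact binomial, X ~ Bin(20, p). The documents give no expected completion rate, so a range of p is shown.

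| True rate p | 3 or fewer (failure rule) | 4 to 15 | Exactly 16 | 17 or more |
|---|---|---|---|---|
| 20% | 41% | 59% | <0.01% | <0.01% |
| 50% | 0.13% | 99.3% | 0.46% | 0.13% |
| 70% | <0.001% | 76% | 13% | 11% |
| 80% | <0.001% | 37% | 22% | 41% |
| 90% | <0.001% | 4.3% | 9.0% | 87% |

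- **Sign.** At p = 80% the chance of passing is 41% under the strict threshold and 41% + 22% = 63% under the other. At p = 90% the figures are 87% and 96%.
- **Failure rule.** At p = 50%, P(X ≤ 3) = (1 + 20 + 190 + 1,140)/2^20 = 1,351/1,048,576 = 0.13%. A session that only half of patients could finish would almost never be called infeasible by this rule.

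**The case against.** The strongest reply is that an 80% benchmark and a 20% failure rule do not contradict each other: one can be a target and the other a floor. That stands. A reader might infer that the two thresholds clash outright, but the text does not support it. A result between them plainly misses the criterion in Purpose of the Study. What is unstated is whether that also makes the protocol infeasible.

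A second reply concerns adherence. A reader might infer that its benchmark also uses a different unit from its failure rule, for example minutes of the session against patients. The documents do not show this. The word degree is ambiguous, and the failure rule, which follows directly, counts patients who complete the exposure. Read as a share of patients, the two agree. The unit clash is therefore established only for data completion.

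Third, the unsigned 80% may be shorthand for the strict threshold used elsewhere, and it matters for a single count. That is fair, but the text does not say so, and at a true rate of 80% that count occurs 22% of the time.

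Finally, this is a descriptive pilot, and observed rates can be reported whatever label is attached. That limits the consequence. It does not remove the inconsistency in rules the plan chose to state.

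**Conclusion.** The point holds as a minor one: the feasibility rules are wrong as written because they are not consistent with each other.

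- The unit clash in data completion is explicit in the text and can produce feasible and not feasible from one dataset.
- The two threshold signs give different answers at 16/20 if the unsigned 80% is read as a benchmark reached.
- The range between the thresholds is a gap in the stated verdict, not a contradiction.

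The probabilities rest on N = 20, on counting per patient, and on assumed true completion rates. The clash in data completion rests on none of these, although its frequency depends on assumed item counts and missingness.

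A reader might also infer that these cut-offs decide whether the later randomized trial goes ahead. No section ties that trial to them; the effect is confined to the Aim 1 conclusion.

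**What to change.** Reconcile Purpose of the Study (Aim 1), Study Measures (Aim 1) and Analyses for Aim 1.

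1. Use one threshold sign in all three places.
2. State that a result short of the benchmark means the feasibility criterion was not met. Then either delete the two sentences with the 20% rule, or label them as a floor and give the verdict for the range between floor and benchmark.
3. Put the data-completion failure rule in the same unit as its benchmark. The smallest change is percent of data collected, the measure already used in all three sections. A patient-level unit is possible, but it is stricter, since one missed item makes a patient incomplete, and it needs a definition of complete.
4. State that adherence is the share of consented patients who complete the 30-minute exposure.

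The change is to wording only, if percent of data collected is kept. The cost is that a result short of the benchmark can no longer be left without a verdict. Counted per patient, a cut at 16/20 is missed 37% of the time at a true rate of 80% and 4.3% at 90%. A cut at 17/20 is missed 59% and 13% of the time. A stated middle verdict would avoid calling a near miss infeasible.

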in two key cognitive variables (i.e., pain catastrophizing, pain self-efficacy) are related to improvements in pain, tension and distress occurring over the VR session. Analyses for Aim 3. Qualitative exit interview data will be coded using open coding and memoing by the study team to generate repeated concepts. These results will be categorized into major themes through selective coding methods. Grounded Theory methods will be used to evaluate the data gathered from the exit interviews.^{40,41} Results will be used to refine and improve the VR protocol for future studies. [name] (co-I) has used Grounded Theory in development of other psychosocial interventions for patients with cancer.

Risk/Benefit Assessment

Risks associated with the proposed study are minimal and not expected, but nonetheless will be carefully monitored. First, due to the use of virtual reality there is the potential for “cybersickness,” a type of motion sickness involving feelings of nausea, eyestrain and/or dizziness. Anticipated risks associated with cybersickness are comparable to typical “everyday” use of computers. If the participant begins to feel any effect of this type, he/she may immediately stop the stop the VR exposure. Patients will be asked to report these symptoms and will have the option of discontinuing participation if these symptoms are problematic. Second, participants may experience anxiety or distress due to questioning about thoughts, feelings, and/or their experience with pain. Again, participants will have the option to discontinue participation if they experience such problems in completing the measures. Third, there is also the possibility of a breach of confidentiality. The informed consent process will address this possibility. All efforts will be made for confidentiality to be maintained by using study ID numbers to identify participants’ research records and by having a limited number of individuals who have access to identifying information. Identifying information will be kept separate from research records. All research records will be kept in a locked file cabinet and password protected computer files. Only the PI and other trained research staff will have access to the research records.

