All patients in the trial will continue their usual medical care during the course of the trial, thus their doctors will provide monitoring of the patients’ overall medical status. Participants will not be asked to change or decline any strategies for pain management.

In terms of study benefits, participants may gain an enhanced ability to cope with pain and pain-related distress as a result of participating in this study. Further, participants may experience decreases in symptom severity.

The proposed significance of study findings outweighs the risks. The long-term goal of this research is to improve quality of life in advanced colorectal cancer patients by decreasing pain, tension and distress. This project will provide preliminary data that will be used to inform and optimize development of a multi-session VR protocol to be tested in patients with advanced stage colorectal cancer that could be generalizable to other palliative care populations with pain.

Data & Safety Monitoring

All research personnel who have direct contact with patients will be trained to observe and report any adverse events and unanticipated problems to the PI ([name]). The PI will review with her mentor, a

senior investigator, and will immediately report any safety/adverse events to the institutional review board at Duke University and to PCRC and NINR. An adverse event is defined as any untoward medical occurrence during the clinical investigation that has a causal relationship to the study protocol. A serious adverse event is defined as any event which results in death, is immediately life threatening, results in persistent or significant disability/incapacity, patient hospitalization, or is serious for any other reason representing significant hazard.

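### The adverse event definition requires causality and the serious adverse event definition does not, so non-serious events judged unrelated can drop out of adverse event reporting

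*Combined protocol and SAP*

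**What the plan says.** In Data & Safety Monitoring, an adverse event is "any untoward medical occurrence during the clinical investigation that has a causal relationship to the study protocol". The sentence after it defines a serious adverse event as "any event which results in death, is immediately life threatening, results in persistent or significant disability/incapacity, patient hospitalization", or an event otherwise representing a significant hazard. That sentence makes no mention of cause.

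Under the same section, staff in contact with patients are "trained to observe and report any adverse events and unanticipated problems to the PI". The PI reviews with a senior mentor and reports onward to the institutional review board and two other named bodies. The section does not say who judges causality, when, or by what criteria.

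The Aim 1 safety outcome is described elsewhere. Study Measures bases it on participants' "report of VR side effects, such as motion sickness, dizziness, headache, nausea, or other negative physical reactions". Data Analysis and Statistical Considerations sets the criterion as "80% of participants completing the VR session without significant side effects". Risk/Benefit Assessment, after naming nausea, eyestrain and dizziness as cybersickness, adds: "Patients will be asked to report these symptoms and will have the option of discontinuing participation if these symptoms are problematic".

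**The concern.** Relatedness is normally a property recorded for each event. Here it is a condition for being an event. Someone must therefore settle the cause before the duty to report an adverse event arises, and an event judged unrelated need not reach the PI and the mentor, who could question that judgement.

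Attribution is hard in this population. Patients have stage IV disease and continue usual care, and Background & Significance lists nausea among the side effects of pain and symptom medication. The study has one group, so no comparator can show how much nausea, dizziness or headache would have occurred without VR. Safety is a named Aim 1 outcome, and the results are meant to inform a multi-session protocol. An adverse event list that omits events judged unrelated cannot later be re-examined for that purpose.

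**Working it through.** **Step 1. Classify events under the two definitions as written.**

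| Event | Adverse event? | Serious adverse event? |
|---|---|---|
| Non-serious, judged related | Yes | No |
| Non-serious, judged unrelated | No | No |
| Serious, judged related | Yes | Yes |
| Serious, judged unrelated | No | Yes |

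The fourth row is the internal conflict: an event can be a serious adverse event without being an adverse event. The second row is the gap: neither definition covers it.

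**Step 2. Ask whether another route covers the second row.** Staff also report unanticipated problems. Risk/Benefit Assessment, however, already names nausea, eyestrain and dizziness as possible effects. An episode of nausea blamed on medication would then be neither an adverse event nor serious, and it would be hard to call unanticipated. That route does not clearly catch it.

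**Step 3. Direction for the adverse event record.** Let A be the number of untoward occurrences and R the number judged related. R counts a subset of A, so R ≤ A always. The clause can remove events from the record and cannot add any. The documents give no rate for A or for the share judged unrelated, so A − R cannot be estimated.

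**Step 4. The Aim 1 benchmark, conditionally.** The documents give N = 20 and 80%. Reading the criterion as at least 80%, 0.80 × 20 = 16, so at most 4 participants may have a significant side effect. The exact 95% CI for 16/20 is 56% to 94%.

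The rest of this step applies only if the causal filter were also used on the participant-reported endpoint, which no section states. All symptom rates and counts in it are assumptions.

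- Suppose 6 of 20 had a significant in-session symptom. Counting all: 14/20 = 70% (exact 95% CI 46% to 88%), below the benchmark. Setting aside 2 of the 6 as unrelated: 16/20 = 80%, benchmark met. Setting aside 3: 17/20 = 85%.
- More generally, let q be the true proportion with such a symptom and m the share of those set aside. The proportion counted as free of side effects is p = 1 − q(1 − m), and the chance of meeting the benchmark is P(X ≥ 16) with X ~ Binomial(20, p).

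| q | m = 0 | m = 0.25 | m = 0.5 |
|---|---|---|---|
| 0.20 | 0.63 | 0.83 | 0.96 |
| 0.30 | 0.24 | 0.52 | 0.83 |
| 0.40 | 0.05 | 0.24 | 0.63 |

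For example, q = 0.30 and m = 0.5 give p = 1 − 0.30 × 0.5 = 0.85 and a chance of 0.83. The table shows why the plan should state its attribution rule. It does not estimate a bias in this trial.

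**The case against.** A reader might infer that in-session symptoms blamed on cancer or its treatment are never recorded, and that the trial's safety result will therefore look too good. The documents do not support either inference.

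- The symptoms that decide the Aim 1 criterion come from participants' own reports, and patients are to be asked about cybersickness symptoms. That route does not depend on the adverse event definition.
- No section carries the causal condition over to the endpoint.
- The direction of any error in the endpoint is not established. No pre-session rating of these symptoms is described, so background nausea could equally be counted against VR.
- The documents do not say that contact staff judge causality, or that this happens before anything is written down.
- The serious adverse event sentence errs towards more capture, so the gap is confined to non-serious events judged unrelated, around a single 30-minute exposure.

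All of this stands, and it limits the point to adverse event reporting. It does not remove the point. The definition still excludes those events, and the route for unanticipated problems does not clearly recover them. Nor is the separate endpoint a complete safeguard. It is worded as VR side effects, which itself suggests attribution; no rule says whether a symptom blamed on medication counts; and the word *significant* is not defined. Deleting the causal clause does not by itself settle those endpoint questions, so the fix must also address how the side-effect count is reported.

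**Conclusion.** The point holds for adverse event reporting. The two definitions are inconsistent on their face. Following the first leaves non-serious events judged unrelated outside what must be reported as adverse events to the PI and the institutional review board. The direction is certain for that record and the size is unknown.

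For the 80% safety criterion, an effect is possible and not shown. It requires the same attribution to be applied to the participant-reported count, and the movement from 70% to 80% or 85% in the illustration rests on that unstated link as well as on assumed counts. The plan should be corrected because the stated rule is faulty and cheap to repair. This is not evidence that the safety result is biased.

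**What to change.** 1. In Data & Safety Monitoring, delete the closing clause of the adverse event definition that requires a causal relationship. Both definitions then start from any event.
2. Record every untoward occurrence from consent to the end of the appointment, whatever its suspected cause.
3. Add relatedness as a separate field on the event form, judged after the event is recorded, and name who judges it and by what criteria.
4. Report all events and related events side by side.
5. In the Aim 1 analysis text, state that the side-effect count will be reported twice: regardless of attribution, and for events judged related. Showing both also keeps background symptoms from being charged to VR without comment.

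The cost is one deleted clause, one form field and a sentence or two of analysis text. The downside is a few more recorded events and possibly a less favourable safety figure.
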